12.2.3. Protocol-Specific Adverse Events of Special Interest

IMGC936 has 1 AESI: IRR. Any symptom or sign occurring within 24 hours of infusion and suggestive of an IRR should be promptly reported as per Section 12.2.5.

Further information on risks can be found in the IMGC936 Investigator's Brochure.

12.2.4. Pregnancy

All reports of pregnancy in participants or partners of male participants must be reported to the sponsor by study-site personnel within 24 hours of their knowledge of the event using the Pregnancy Exposure Form. Abnormal pregnancy outcomes (eg, spontaneous abortion, fetal death, stillbirth, congenital anomalies, ectopic pregnancy) are considered SAEs and must be reported using the SAE report form. Any participant who becomes pregnant during the study must discontinue further study drug administration.

Because the effect of the study drug on sperm is unknown, pregnancies in partners of male participants included in the study will be reported by the study-site personnel within 24 hours of

their knowledge of the event. If the female partner of a male participant becomes pregnant, the partner must be requested to complete a Pregnant Partner Consent Form so that pregnant partner, fetal, and/or newborn information can be collected.

Upon confirmation of serum or urine pregnancy testing, the participant will be followed for the outcome of pregnancy. Follow-up information will be collected for all live newborns at birth and 6 months after the birth. All necessary information will be collected to assess the effects of study drug on the newborn. If necessary, the follow-up period will be extended for the newborn.

12.2.5. Reporting of Adverse Events to the Sponsor

The investigator must document all AEs in eCRFs in a timely manner. Refer to Table 10 for reporting timeframes.

Note: When reporting an AESI, complete the SAE/AESI form, stating that the event is an AESI.

Table 10: Safety Reporting by Event Type

Type of Event:	Hard Copy Form/Timeline for Reporting	eCRF Timeline for Data Entry
Serious adverse event (SAE)	SAE/AESI form within 24 hours of awareness	Within 5 calendar days of awareness
Pregnancy	Pregnancy exposure form within 24 hours of awareness	Within 5 calendar days of awareness
AESI	SAE/AESI form within 24 hours of awareness	Within 5 calendar days of awareness

Abbreviations: AESI: adverse event of special interest; eCRF: electronic case report form; SAE: serious adverse event.

13. PRODUCT QUALITY COMPLAINT HANDLING

A product quality complaint (PQC) is defined as any suspicion of a product defect related to manufacturing, labeling, or packaging, ie, any dissatisfaction relative to the identity, quality, durability, or reliability of a product, including its labeling or package integrity. A PQC may have an impact on participant safety and activity of the product. Timely, accurate, and complete reporting and analysis of PQC information from studies are crucial for the protection of participants, investigators, and the sponsor and are mandated by regulatory agencies worldwide. The sponsor has established procedures in conformity with regulatory requirements worldwide to ensure appropriate reporting of PQC information; all studies conducted by the sponsor or its affiliates will be conducted in accordance with those procedures.

13.1. Procedure

All initial PQCs must be reported to the sponsor by the study-site personnel, after being made aware of the event, and those that are associated with clinical consequences must be reported within 24 hours.

If the defect is combined with a SAE, the study-site personnel must report the PQC to the sponsor according to the SAE reporting timelines (refer to Section 12.2.2, Serious Adverse Events). A sample of the suspected product should be maintained for further investigation if requested by the sponsor.

13.2. Contacting Sponsor Regarding Product Quality

Name(s) and corresponding telephone numbers of the individuals who should be contacted regarding product quality issues are listed on the contact information page(s), which will be provided as a separate document.

14. STATISTICAL ANALYSIS

This section outlines the statistical methodology and principles which will be used for data analysis in this study. A separate statistical analysis plan (SAP) will further describe the details regarding statistical methods and will govern the analysis.

14.1. Determination of Sample Size

The number of participants who receive study drug cannot be determined precisely in advance. The study plans to treat up to approximately 72 participants in dose escalation. The sample size is based on a 3 + 3 design with 7 planned dose cohorts of IMGC936. Additional participants may be enrolled if a dose cohort is expanded, participants are replaced, or intermediate dose levels are evaluated

Each expansion cohort may be expanded independently following an optimal Simon's 2-stage design. The null hypothesis is that an uninteresting response rate is 9% less. The design has 80% power to detect a target response rate of 25% at the significance level of 1-sided 0.05. Following this design per cohort, the first stage of the futility assessment will be conducted in the first 13 response-evaluable participants in each expansion cohort. If no more than 1 responder is observed in an expansion cohort, no further participants will be recruited to that cohort and the null hypothesis will not be rejected. If there are at least 2 responders out of the 13 response-evaluable participants at the first stage, each may enroll an additional 26 participants to that cohort. If there are at least 7 responders out of a total of 39 response-evaluable participants, the null hypothesis will be rejected for that cohort.

14.2. Analysis Populations

The study analyses will be performed on the following populations:

- Safety Population: All participants who received at least one dose of study drug. This population will be used for analyses of safety, PK, and immunogenicity. It will also be used for summary of baseline data and analyses of PFS.
- Response Evaluable Population: All participants who received at least one dose of study drug, had baseline measurable or non-measurable disease, and had at least one post-baseline radiographic tumor assessment or discontinued study drug due to clinical progression or death if no post-baseline tumor assessment. This population will be used for summary of tumor assessment data and analyses of response rates.

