5.1. Inclusion Criteria

- 1. Ability to provide informed consent and documentation of informed consent prior to any study-related tests or procedures that are not part of standard of care for the participant's disease. Participants must be willing and able to comply with study procedures.
- 2. Participants with histologically proven, relapsed or refractory, unresectable locally advanced or metastatic non-squamous NSCLC, TNBC, CRC, gastroesophageal cancer, or pancreatic cancer for whom no therapy with demonstrated clinical benefit is available. Participants in expansion cohorts must have received all appropriate approved therapy and fit within the prior lines of therapy restrictions listed below.

Note: Neoadjuvant/adjuvant systemic treatment are included as 1 line in prior lines of therapy, except for TNBC where they are excluded.

Note: Maintenance therapies are considered part of the prior line of therapy and will not be counted as a separate line of therapy.

- a. Non-squamous NSCLC: Participants in dose expansion phase may have been treated with up to 3 prior lines of systemic chemotherapy, with no limit on prior targeted therapy containing lines, eg, for targetable mutations.
- b. TNBC: Participants in dose expansion phase may have been treated with up to 4 prior lines of systemic therapy for metastatic disease, excluding checkpoint inhibitors and neoadjuvant/adjuvant therapies.
- c. CRC: Participants in dose expansion phase may have been treated with up to 4 prior lines of systemic therapy.
- d. Gastroesophageal cancer: Participants in dose expansion phase may have been treated with up to 4 prior lines of systemic therapy.
- e. Pancreatic cancer: Participants in dose expansion phase must have been treated with 1 to 3 prior lines of systemic therapy, with no more than 2 chemotherapy-containing lines.
- 3. Either non-measurable or measurable disease per RECIST v1.1 and documented by computed tomography (CT) and/or magnetic resonance imaging (MRI) obtained within 28 days of Cycle 1 Day 1.
 - a. Dose Escalation Phase: Participants may have non-measurable or measurable disease per RECIST v1.1.
 - b. Dose Expansion Phase: Participants must have measurable disease per RECIST v1.1.
- 4. Age \geq 18 years old.
- 5. Tumor tissue must be submitted. If archival tissue (formalin-fixed paraffin-embedded [FFPE] block or slides) is not available, participants may undergo a low-risk, medically routine procedure, if appropriate.

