2.1 Assessment of Overall Tumor Burden and Measurable Disease

To assess objective response or future progression, it is necessary to estimate the *overall tumor burden at baseline* and use this as a comparator for subsequent measurements. Only participants with measurable disease at baseline should be included. Measurable disease is defined by the presence of at least one measurable lesion (as detailed above).

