2.3.1 Evaluation of Target Lesions

Complete Response (CR): Disappearance of all target lesions. Any pathological lymph nodes (whether target or non-target) must have reduction in short axis to < 10 mm.

Partial Response (PR): at least a 30% decrease in the sum of diameters of target lesions, taking as reference the baseline sum diameters.

Progressive Disease (PD): at least a 20% increase in the sum of diameters of target lesions, taking as reference the *smallest sum on study* (this includes the baseline sum if that is the smallest on study). In addition to the relative increase of 20%, the sum must also demonstrate an absolute increase of at least 5 mm. (*Note:* the appearance of one or more new lesions is also considered progression).

Stable Disease (SD): Neither sufficient shrinkage to qualify for PR nor sufficient increase to qualify for PD, taking as reference the smallest sum diameters while on study.

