2.3.3 Evaluation of Non-target Lesions

This section provides the definitions of the criteria used to determine the tumor response for the group of non-target lesions. While some non-target lesions may be measurable, they need not be measured and instead should be assessed only *qualitatively* at the time points specified in the protocol.

Complete Response (CR): Disappearance of all non-target lesions. All lymph nodes must be non-pathological in size (< 10 mm short axis).

Non-CR/Non-PD: Persistence of one or more non-target lesions(s).

Progressive Disease (PD): Unequivocal progression (see comments below) of existing non-target lesions. (*Note*: the appearance of one or more new lesions is also considered progression).

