2.4.1 Time Point Response

It is assumed that at each protocol specified time point, a response assessment occurs. Table A-1 provides a summary of the overall response status calculation at each time point for participants who have measurable disease at baseline.

ImmunoGen, Inc 29 March 2022

IMGC936 Clinical Study Protocol: IMGC936-0901 Amendment 3

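### In dose escalation, the ORR denominator admits participants with only non-measurable disease, who can respond only by confirmed CR and whose best overall response is not fully defined

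*Protocol*

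**What the plan says.** - **Population.** Protocol 14.2 and SAP 4.11.2 use the same baseline condition: a response-evaluable participant "had baseline measurable or non-measurable disease". Protocol 14.7.1 and SAP 6.1.3, read with the opening of SAP section 6, divide the number with a best overall response (BOR) of CR or PR by this population.
- **Eligibility.** Inclusion criterion 3 in Protocol 5.1 separates the phases: "Dose Escalation Phase: Participants may have non-measurable or measurable disease per RECIST v1.1", but "Dose Expansion Phase: Participants must have measurable disease per RECIST v1.1".
- **RECIST appendix.** Appendix 6 section 2.1, on assessing objective response or future progression, states: "Only participants with measurable disease at baseline should be included". Section 2.3.1 defines PR as "at least a 30% decrease in the sum of diameters of target lesions". Section 2.3.3 gives non-target disease three outcomes: CR ("Disappearance of all non-target lesions"), Non-CR/Non-PD, and PD. Section 2.4.1 says that Table A-1 serves "participants who have measurable disease at baseline".
- **BOR categories.** Protocol 14.7.1 lists CR, PR, SD, PD and NE. SAP 6.1.2 ranks CR, PR, SD and PD, and assigns NE when there is no post-baseline response assessment.
- **Supporting analyses.** SAP 6.4 plans no efficacy subgroups and SAP 6.5 no sensitivity analyses.

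**The concern.** A participant with no measurable lesion has no target lesions, and so no sum of diameters that could fall by 30%. That participant enters the ORR denominator like any other but can enter the numerator by only one route, a confirmed CR. The escalation ORR then depends partly on how many such participants happen to be enrolled.

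ORR is a secondary endpoint of escalation (Protocol 3.1.2). Dose levels may be enlarged to 15 participants partly to look at antitumor activity (Protocol 4.4). In groups of that size, two or three participants with non-measurable disease only can visibly move the percentage.

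There is also a gap in definition that does not depend on the size of the ORR effect. If non-target lesions persist without progressing, Appendix 6 calls the result Non-CR/Non-PD, but no BOR category carries that name. Whoever programs the table must choose between SD and NE without a rule.

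**Working it through.** **1. Where the population clause matters.** Criterion 3 requires measurable disease in expansion, so admitting non-measurable disease has no effect there unless an ineligible participant is enrolled. In escalation the same clause does have effect.

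**2. The plan's own figure for this population.** The only design calculation that uses response-evaluable participants is the expansion Simon design in Protocol 14.1: 13 participants, continue with at least 2 responders, then 39 in total, reject the null with at least 7; null rate 9%, target rate 25%. With X1 the responders among the first 13 and X2 those among the next 26, the probability of rejection is

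Σ over x ≥ 2 of P(X1 = x) × P(X2 ≥ 7 − x).

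- At 9%: 0.0454, within the stated one-sided 0.05.
- At 25%: 0.809, against the stated 80%.

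The design reproduces. By step 1 it does not change.

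**3. Routes to response without measurable disease.** The PR definition in section 2.3.1 needs target lesions, so it cannot be met. CR can be met under section 2.3.3 if every non-target lesion disappears. Section 2.3.4 does discuss participants with non-measurable disease only, but only for judging progression.

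**4. Dilution formula.** Let m be the ORR in measurable disease, c the confirmed CR rate in non-measurable-only disease, and f the share of response-evaluable escalation participants with non-measurable disease only. Then

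reported ORR = (1 − f) × m + f × c,

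and the shortfall against m is f × (m − c). It is zero if f = 0 or c = m, and positive if f > 0 and c < m.

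**5. Illustrations.** The documents give no value of f, m or c for escalation, so all of these are assumptions. The values 9% and 25% are borrowed from the expansion design.

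| m | c | f = 5% | f = 10% | f = 20% | f = 30% |
|---|---|---|---|---|---|
| 20% | 0% | 19.0% | 18.0% | 16.0% | 14.0% |
| 25% | 0% | 23.75% | 22.5% | 20.0% | 17.5% |
| 25% | 5% | 24.0% | 23.0% | 21.0% | 19.0% |
| 9% | 0% | 8.55% | 8.1% | 7.2% | 6.3% |

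From m = 25%, the shortfall runs from 0.05 × (25 − 5) = 1.0 point to 0.30 × (25 − 0) = 7.5 points.

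**6. The same effect in counts, with exact 95% intervals.**

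- Dose level of 15, three with non-measurable disease only, 3 responders, all with measurable disease: 3/15 = 20.0% (4.3 to 48.1) against 3/12 = 25.0% (5.5 to 57.2).
- All 72 escalation participants pooled, 14 with non-measurable disease only, 14 responders, all with measurable disease: 14/72 = 19.4% (11.1 to 30.5) against 14/58 = 24.1% (13.9 to 37.2).

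**The case against.** The strongest reply is that the inclusive denominator is deliberate. Protocol and SAP agree on it, it matches the escalation eligibility rule, and the SAP governs the analysis. Appendix 6 is adapted guideline text rather than a definition of an analysis population. Its measurable-disease sentence also covers progression, yet section 2.3.4 of the same appendix tells the reader how to judge progression in non-measurable disease. On this view the ORR simply describes response among everyone evaluable. Much of this stands: the documents do not show that the population was set by mistake, and the conflict is one of wording to be reconciled. It does not answer the missing BOR category, nor the fact that one group in the denominator has no route to PR.

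Imprecision is a second reply, and it is also fair. In both count examples the intervals overlap heavily, and the escalation ORR is descriptive.

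Four stronger readings may tempt a reader, and the documents do not support them:

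- *These participants are automatic non-responders, so the ORR is certainly biased downward.* A confirmed CR remains possible, and the effect is zero if none enrol.
- *The denominator distorts dose selection.* Escalation runs on DLT counts. Protocol 4.4 names response data for choosing the MAD if escalation stops before an MTD, and all available data for the RP2D, but it does not name the ORR percentage or this population. SAP section 7 already names 6 mg/kg as the combined recommended dose.
- *It spoils a comparison between escalation and expansion.* None is planned, and the phases also differ in prior-therapy limits, tumor mix and dose.
- *It undermines the primary endpoint.* Expansion requires measurable disease.

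**Conclusion.** The point holds for dose escalation only. Participants with non-measurable disease only are counted in the ORR denominator and can be responders only through a confirmed CR. The escalation ORR is diluted by f × (m − c) if such participants enrol and their CR rate is below the ORR in measurable disease. That condition is the expected case, but it is an assumption. The documents do not fix the size: with the assumed values above it runs from about 1 to 7.5 points off a 25% ORR, and it may be zero.

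Two defects do not depend on that size. The population definition and Appendix 6 section 2.1 give different answers to who is assessed for objective response. And neither Table A-1 nor the BOR categories classify a participant whose disease is entirely non-target. No planned analysis covers either gap. This is worth correcting because it is cheap and affects a secondary endpoint; it does not threaten the trial's primary efficacy conclusion.

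**What to change.** 1. Reconcile Protocol 14.2 and SAP 4.11.2 with Appendix 6 section 2.1, so that one rule states who is assessed for objective response in escalation.
2. In SAP 4.11.2 and 6.1.3, calculate the escalation ORR in participants with measurable disease at baseline, and show the all-evaluable ORR beside it. Restriction alone would drop a confirmed CR in a participant with non-measurable disease only; the second row keeps it visible.
3. Add Non-CR/Non-PD to the BOR categories in Protocol 14.7.1 and SAP 6.1.2 for participants with non-target disease only, and state the time-point rule that Table A-1 lacks.
4. In Protocol 14.7.2 and SAP 6.2, limit the spider and waterfall plots to participants with target lesions, since both plot the sum of target-lesion diameters.

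The cost is one baseline flag, one extra table row, one extra response category and slightly smaller escalation denominators. Enrolment, assessments and the expansion design stay as they are.

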14.3. Demographics and Baseline Characteristics

Participant disposition, demographics, baseline characteristics, disease history, medical history, and prior cancer treatment will be summarized using descriptive statistics.

14.4. Study Drug Exposures and Concomitant Medications

Study drug exposures and concomitant medications will be summarized by descriptive statistics. The summary of study drug exposure will include descriptive statistics as well as frequency counts for the number of doses or cycles received, the total dose administered as well as the total

dose intended, and the dose intensity, which is calculated as percentage of total dose actually administered divided by total dose intended during the whole treatment period.

14.5. Safety Endpoints and Analyses

14.5.1. Adverse Events

Only treatment-emergent AEs will be summarized in tables. The following AEs will be provided in summary tables as well as displayed in listings:

- All AEs
- AEs with CTCAE severity Grade ≥ 3
- Ocular AEs
- Study drug related AEs
- Study drug related AEs with CTCAE severity Grade ≥ 3
- SAEs
- Study drug related SAEs
- AEs resulting in discontinuation of study drug
- AEs resulting in interruption of study drug
- Study drug related AEs resulting in discontinuation of study drug
- Study drug related AEs resulting in interruption of study drug
- Fatal AEs
- AESIs

All of these tables will display the number and percent of participants that experience the given event and will display events by Medical Dictionary for Regulatory Activities (MedDRA) system organ class (SOC) and preferred term (PT). Events will be displayed alphabetically for SOC and in descending order of overall PT incidence within each SOC. An overall summary of AEs will display the number and percent of participants who experience at least one event of each of the above types.

14.5.2. Laboratory Values

Summaries of laboratory values will display descriptive statistics for numerically quantified laboratory test results. Summaries will be grouped by laboratory panel (eg, hematology, blood chemistry, and urinalysis) and will be displayed by visit for each laboratory parameter.

14.5.3. Other Safety Endpoints

Twelve lead ECGs will be collected and analyzed for evidence of cardiac toxicity, especially prolongation of QT interval. Change in LVEF from baseline will be summarized. Vital signs will be summarized with descriptive statistics at each visit and time point at which they are collected. Shift tables may be created.

14.6. Pharmacokinetic Biomarker Analysis

14.6.1. Pharmacokinetic Analysis

Study drug concentrations will be summarized. Summary statistics will be tabulated separately for PK parameters by IMGC936 dose. Geometric means and percent coefficients of variation will be reported for C_{max} , AUC from time zero to time t (AUC_{0-t}), AUC_{0-inf}, trough concentration (C_{trough}) and accumulation index (AI); arithmetic means and standard deviations will be reported for half-life ($t_{1/2}$), clearance (CL), and volume of distribution at steady state (V_{ss}); and medians, minimum, and maximum will be reported for time to maximum concentration (T_{max}). Separate scatter plots of C_{max} and AUC may be provided versus dose to assess dose dependency. Dose proportionality may be assessed using a power model.

14.6.2. Immunogenicity Analysis

The proportion of participants who are negative for ADAs at baseline and become positive in this assay, the proportion of participants who are negative at baseline and remain negative, and those who have positive ADA at baseline that increases or decreases in titer over the course of the study will be summarized.

14.6.3. Biomarker Analysis

Summary statistics for biomarker parameters, such as, but not limited to, those listed in Section 10.3 and corresponding changes from baseline will be summarized and/or may also be presented graphically. Biomarker analysis and subsequent results may be reported in separate documents and not included in the SAP or clinical study report, respectively.

